6.4 Dispensing

All dosing will be on an outpatient basis. Study drug will be first dispensed to subjects/caregivers on Day 1 (Baseline, Visit 1); enough study drug will be dispensed to last the subject until Visit 3.

Thereafter, study drug will be dispensed at Week 13 (Visit 3) and at each subsequent study visit so long as the subject will continue on study drug. The supplies dispensed to a subject at each of these times will be sufficient to allow for intake of the necessary number of tablets for the scheduled number of days, with additional supplies as overage in the event of a delay in the visit. Subjects should bring all study medication, including the overage supply, with them to the Week 13 visit (Visit 3) and to each study visit thereafter during the treatment period for compliance assessment.

Subjects and caregivers will be provided with information about storage conditions and taking study drug, including instructions indicating that study drug must be used only as described in this protocol. They will be informed that subjects are to take each dose of study medication with water and that the tablets may be taken with or without meals. They will also be informed that tablets should be swallowed whole and not broken, crushed, or chewed or dissolved in fluids prior to ingestion (see Section 6.2). In the event of interruption or dose reduction or increase, the subjects and caregivers will be provided with updated dosing instructions.

6.5 Compliance

Subject compliance with prescribed dose of study drug will be assessed by questioning the subject and caregiver at the Week 2 visit (Visit 2) and at each study visit thereafter during the treatment period.

At the Week 13 visit (Visit 3) and at each study visit thereafter during the treatment period, the subject/caregiver will bring all unused study drug to the study site. The number of tablets (all tablets remaining in the bottle plus any tablets that have been removed from the bottle) will be counted and recorded by study site staff. Empty bottles and packaging should also be returned by the subject/caregiver to the study site. At each post-Baseline visit beginning with the Week 13 visit (Visit 3), the number of tablets dispensed to the subject/caregiver will also be recorded.

Any apparent discrepancies between the number of tablets taken and the number of tablets which should have been taken since the last visit will be discussed with the subject and caregiver. Compliance data obtained at Visit 2 and each study visit thereafter, including dates of any dose deviations and/or interruptions, and any other pertinent

information, will be recorded in the source documentation and on the appropriate field of the eCRF based on the investigator determination.

If during participation in the study a subject's compliance is determined to be < 80% or > 120% (taking into consideration allowable reductions/increases determined and recorded by the investigator in the number of tablets taken, or dose interruptions), the subject and caregiver should be reeducated about taking study drug properly and the clinical research associate should be informed promptly. If compliance problems are recurrent, the investigator should inform the clinical research associate and contact the medical monitor to determine the course of action.

6.6 Accountability

The investigator or designee will keep a record of all study drug received, and of all study drug dispensed to and returned by subjects.

The investigator will ensure that the supplied study drug will be used only for administration to subjects enrolled in this study and for no other purpose.

The study drug accountability record will be checked by a study monitor at monitoring visits.

All unused and returned study drug will be either returned to the Sponsor or designee or disposed of after study completion according to provided instructions.

7 ASSESSMENT OF SAFETY

Safety will be assessed over time by means of adverse events (AEs) and concomitant medication recording; clinical laboratory tests of blood (*e.g.*, hematology and chemistry panels); vital sign measurements; 12-lead ECGs; and targeted physical and neurological examinations.

Assessments to be performed in the clinic are described in the subsections that follow. At an intervening time between Visit 2 and Visit 3 (approximately 6 weeks after Baseline), caregivers of subjects are to be contacted by telephone. An unscheduled visit is to take place if needed in response to a safety concern.

7.1 Adverse Events

An AE is any unfavorable or unintended sign, symptom, or disease, whether or not considered related to the study treatment. This also includes events resulting from medication error or inappropriate use. Recording of new AEs and changes to ongoing AEs will begin at the time the ICF is signed using the eCRF mapped from the double-blind study of original participation. AEs will be ascertained by asking the subject (and caregiver) how the subject has been since the last visit. A clinical abnormality or laboratory test value abnormality that the investigator deems to be clinically significant should be recorded as an AE.

Every attempt should be made to describe the AE in terms of a diagnosis. Once a clear diagnosis has been made, individual signs and symptoms shall not be recorded unless they represent atypical or extreme manifestations of the diagnosis, in which case they

should be reported as separate events. Events and signs/symptoms leading up to a diagnosis should be retained. If a clear diagnosis cannot be established, each sign and symptom must be recorded individually.

All AEs must be fully recorded in the source documents and in the eCRF, regardless of whether or not the event is considered related to study drug.

For all AEs, the investigator must pursue and obtain information adequate both to determine the outcome of the AE and to assess whether it meets the criteria for classification as a Serious Adverse Event (SAE) or pregnancy requiring immediate notification (see Sections 7.1.4 and 7.1.5).

Follow-up of an AE, even after the final dose of study drug, is required if the AE or its sequelae persist. Follow-up is required, including beyond the scheduled final off-treatment visit if needed, until the AE or its sequelae resolve or stabilize at a level acceptable to the investigator.

For each AE, information recorded will include the following: the date when the AE started, the date when the AE stopped (or whether it remained ongoing), the intensity of the AE (see Section 7.1.1), the relationship of the AE to study drug (see Section 7.1.2), action taken with regard to study drug (none, dose reduction, interrupted, or discontinued), other drug therapy (no change, new medication, altered medication, or both of the latter), outcome, and whether or not the AE was considered an SAE (see Section 7.1.4).

7.1.1 Intensity

The intensity (severity) of each AE will be assessed by the investigator and graded as mild, moderate, or severe, as follows:

- Mild: An AE that is easily tolerated by the subject, causes minimal discomfort and does not interfere with everyday activities
- Moderate: An AE that is sufficiently discomforting to interfere with normal everyday activities
- Severe: An AE that prevents normal everyday activities

7.1.2 Relationship to Study Drug

The investigator will make a judgment considering whether or not, in his or her opinion, each AE is related to the study drug according to classifications described here. However, even if the investigator feels that there is no relationship to the study drug, the AE should be reported nevertheless. For each AE, the relationship or association (causality) of the AE to study drug will be assessed by the investigator and characterized as not related, unlikely related, possibly related, or related as follows:

- Not related: If there is a confirmed cause of the AE (other medical condition, other therapy) which does not involve the study drug
- Unlikely related: If the temporal association between the AE and the study drug is such that the AE is not likely to be related to the study drug

- Possibly related: If the AE shows a reasonable temporal association to study drug administration but could be due to the subject's clinical state or other therapies administered
- Related: If the AE shows a reasonable temporal association to study drug administration and cannot be explained by the known characteristics of the subject's clinical state

7.1.3 Adverse Events of Special Interest

The following adverse events are of special interest because additional steps are to be taken by the investigator to assess and manage them. The medical monitor shall be informed (either directly by the laboratory or the site, depending on the nature of the event). AESIs include:

- Signs or symptoms consistent with hemolytic anemia (see Section 7.1.3.1)
- A case clinically judged to possibly represent serotonin syndrome (see Section 7.1.3.2)

See Section 6.2.3 for additional details regarding dose interruption, reduction, or discontinuation in response to these AESIs.

Each AESI should be recorded as for any other adverse event.

7.1.3.1 Hemolytic Anemia

The subject should be evaluated at each visit for possible clinical symptoms associated with hemolytic anemia, in conjunction with review of hematology results. Should hemolytic anemia be suspected, follow-up testing should be performed as described in Section 7.3.2. The medical monitor should be contacted to discuss whether or not resumption of dosing is indicated or for any other questions.

The signs and symptoms of anemia include:

- Cyanosis, headache, anxiety, exercise intolerance, fatigue, confusion, dizziness, tachypnea, palpitation, dysrhythmia, seizures, and coma

Signs of possible hemolytic anemia include:

- Decrease by 20% from Baseline in RBC count and/or hemoglobin
- Abnormal RBCs in peripheral blood smear
- Elevation of reticulocyte count to above laboratory normal range
- Increase in LDH or indirect bilirubin, or low haptoglobin

7.1.3.2 Serotonin Syndrome (Toxicity)

Subjects are to be monitored for signs and symptoms indicative of potential serotonin toxicity, especially when initiating LMTM in this study or any medication with serotonergic potential. At each post-Baseline visit, subjects are to be evaluated by a medically qualified person by targeted physical and neurological examination and measurement of temperature, respiratory rate, blood pressure, and pulse. Results of the MMSE should also be taken into consideration. The evaluation should focus on detecting

signs and symptoms of serotonin syndrome (or serotonin toxicity) that include mental changes (confusion, hyperactivity, memory problems not attributed to underlying condition), muscle twitching, excessive sweating, shivering or shaking, diarrhea, trouble with coordination, and/or fever. A further guide is provided below.

Table 7-1 Overview of Monitoring and Management of Serotonin Syndrome (Toxicity)

Signs and Symptoms of Serotonin Toxicity	Monitoring at Each Clinic Visit	Action

Any one of the following:
 
Autonomic findings (temperature ≥ 38 °C, diaphoresis, shivering, tachypnea/dyspnea, diarrhea, hypertension or hypotension)
 
Neuromuscular changes (tremor; hyperreflexia; spontaneous, inducible, or ocular clonus; muscle rigidity¹; hypertonia; dizziness; incoordination; or mydriasis)
 
Other central nervous system changes (agitation/akathisia, elevated mood, insomnia)
	Oral (sublingual) temperature ²	
Discontinue study drug
 
Appropriate medical management to be undertaken
 
Report to Medical Monitor as AESI

	Seated blood pressure and pulse	
	Targeted PE and neurological examination, focused on the following: deep-tendon reflexes, clonus, and muscle rigidity; size and reactivity of pupils; dryness of oral mucosa; intensity of bowel sounds; skin color; and presence or absence of diaphoresis	
	MMSE (Baseline ³ , Weeks 26, 52, at the 4-week follow-up visit, and as needed to respond to changes)	

¹ Muscle rigidity can overwhelm other neuromuscular findings and mask the diagnosis

² Oral (sublingual) temperature measurements are preferable; aural temperature is an acceptable alternative (use of alternate measurement is to be noted in the eCRF)

³ MMSE to be rated at Baseline if not available from within the prior 42 days in the previous study of participation

Should serotonin syndrome (toxicity) be suspected clinically, “serotonin toxicity” should be recorded as the adverse event rather than the individual signs or symptoms. These should be indicated by answering “yes” or “no” to each of the signs and/or symptoms indicated on the form provided in the eCRF. These signs and symptoms, based on physical and neurological examination, include the following: abnormal conscious level (delirium), agitation or akathisia, elevated mood, insomnia, myoclonus, tremor, mydriasis, nystagmus, clonus, hyperreflexia, hypertonia (rigidity), dizziness, incoordination, shivering, diaphoresis (sweating), diarrhea, pyrexia (fever), tachycardia, tachypnea or dyspnea, hypertension or hypotension. An “other” field should also be included in the eCRF to indicate any additional findings.

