6.2.3.1 Hemolytic Anemia

When there are clinical symptoms and/or laboratory signs of hemolytic anemia, dosing should be discontinued. Clinical symptoms are described in Section 7.1.3.1 and laboratory signs are described in Section 7.3.2. Follow-up laboratory monitoring is also

⁵ Administrative reasons (or other reasons not related to safety) are not to be considered safety reasons warranting treatment discontinuation.

described in Section 7.3.2. The medical monitor should be contacted to discuss whether or not resumption of dosing is indicated or for any other questions.

6.2.3.2 *Serotonin Syndrome*

Subjects are to be monitored at each visit by a medically qualified person for signs and symptoms indicative of potential serotonin toxicity, especially when initiating LMTM in this study or any medication with serotonergic potential. At each post-Baseline visit, subjects are to be evaluated by targeted physical and neurological examination and measurement of temperature, respiratory rate, blood pressure, and pulse (see Section 7.1.3.2 for guidance on assessment). Should serotonin syndrome (toxicity) be suspected clinically, treatment should be immediately discontinued. The event should be reported as an AESI and the medical monitor should be contacted for further guidance on subject management.

6.2.3.3 *Other Safety Reasons Requiring Dose Adjustment*

Treatment should be discontinued if the following treatment-emergent change occurs on ECG (based on the means of the three recordings) without other explanatory cause:

- QTcF interval > 500 msec: repeat ECGs should be obtained, in triplicate, within 2 weeks; if confirmed by the mean of the repeat ECGs, study drug should be discontinued pending further evaluation.

Other clinically significant changes in the ECG should be discussed with the medical monitor.

If renal concerns arise and the calculated creatinine clearance is < 30 mL/min, study drug should be discontinued.

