**Table 14.3.4.4.1**  
**Serotonin Toxicity (Syndrome) Assessment by Visit**  
**Safety Population**

	Time point	AD (N= )	bvFTD (N= )	All Subjects (N= )
Sign or Symptom of Serotonin Toxicity (Syndrome) Exhibited 	Baseline	(n= ) n (%)	(n= ) n (%)	(n= ) n (%)
	Week 2	(n= ) n (%)	(n= ) n (%)	(n= ) n (%)
	...			

Note: Baseline is defined as the last non-missing value prior to first dose of study drug.

 Subjects are counted if they answered “yes” to any of the signs or symptoms on the Serotonin Toxicity (Syndrome) Assessment form.

path\t\_program.sas date time

*Programming note: Table will include all target visits and Last Available On-Treatment Value. Please see Appendix A for target visits and visit windows.*

*Programming Note: Repeat table for Table 14.3.4.4.2 Serotonin Toxicity (Syndrome) Assessment by Visit – Non-AChEI/Memantine Users (Safety Population)*

**Table 14.3.4.5.1  
Central ECG Data by Visit  
Safety Population**

ECG Parameter	Time Point	AD (N= )	bvFTD (N= )	All Subjects (N= )
Ventricular Rate (bpm)	Baseline 			
	N	n	n	n
	Mean (SD)	xx.x (xx.xx)	xx.x (xx.xx)	xx.x (xx.xx)
	Median	xx.x	xx.x	xx.x
	Min, Max	xx, xx	xx, xx	xx, xx
	Week 26			
	N	n	n	n
	Mean (SD)	xx.x (xx.xx)	xx.x (xx.xx)	xx.x (xx.xx)
	Median	xx.x	xx.x	xx.x
	Min, Max	xx, xx	xx, xx	xx, xx
	Change from Baseline to Week 26			
	N	n	n	n
	Mean (SD)	xx.x (xx.xx)	xx.x (xx.xx)	xx.x (xx.xx)
	Median	xx.x	xx.x	xx.x
	Min, Max	xx, xx	xx, xx	xx, xx
...				
PR Interval (msec)				
...				

 Baseline is defined as the mean of the last non-missing triplicate values prior to first dose of study drug.  
Note: The summaries are based on the measurements from central read (BIOCLINICA).

path\t\_program.sas date time

*Programming note: table will include all target visits and Last Available On-Treatment Value and the following ECG parameters: Ventricular Rate (beats/min), PR Interval (msec), QRS Duration (msec), QTcB Interval (msec), QTcF Interval (msec). See Appendix A for visit windows.*

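### Protocol Table 7-1 and Sections 6.2.3, 6.2.3.2, 7.1.3 and 7.1.3.2 give different triggers for stopping drug and reporting serotonin toxicity as an AESI, and none is said to prevail

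*Protocol*

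**What the plan says.** Table 7-1 in Protocol Section 7.1.3.2 has a single row.

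- The first column opens with "Any one of the following" and lists autonomic, neuromuscular and other central nervous system findings. The last group reads "Other central nervous system changes (agitation/akathisia, elevated mood, insomnia)".
- The middle column sets out what is monitored at every clinic visit.
- The action column includes "Discontinue study drug" and "Report to Medical Monitor as AESI".

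The sentence that introduces the table says "A further guide is provided below".

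The other passages use different conditions:

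- **Section 6.2.3.2:** "Should serotonin syndrome (toxicity) be suspected clinically, treatment should be immediately discontinued". The event so suspected is then the one to report as an AESI.
- **Section 7.1.3:** the AESI is "A case clinically judged to possibly represent serotonin syndrome". This section sets no stopping trigger of its own and refers to Section 6.2.3 for dosing.
- **Section 7.1.3.2, after the table:** the adverse event term is serotonin toxicity, again on condition of clinical suspicion.
- **Section 6.2.3, introduction:** the AESI is worded as findings that fit the syndrome, with no mention of clinical judgment.

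**The concern.** The same two actions, stopping drug and reporting an AESI, are tied to a single listed sign in one place and to a clinician's suspicion of a syndrome in another. A site that works from the table and a site that works from Section 6.2.3.2 could treat the same subject differently.

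For the subject, the consequence can last. Under Section 4.1, someone who does not complete the first 12 months cannot receive treatment in any later extension period, and continued access to therapy is one of the two primary objectives. There is a risk in the other direction too: one site may continue drug where the table, taken literally, says to stop.

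For the analysis, long-term safety and tolerability is the other primary objective. SAP Section 7.1 tabulates the AESIs that the protocol specifies and the adverse events that lead to dose change or withdrawal. Both depend on which passage a site followed.

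**Working it through.** The plan gives no figure to reproduce, so the check is a comparison of text.

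**Step 1. Count the findings that satisfy the table.** Paired entries such as tachypnea/dyspnea, and the three forms of clonus, count once each.

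- Autonomic, 6: raised temperature, diaphoresis, shivering, tachypnea/dyspnea, diarrhea, hypertension or hypotension.
- Neuromuscular, 8: tremor, hyperreflexia, clonus, rigidity, hypertonia, dizziness, incoordination, mydriasis.
- Other central nervous system, 3: agitation/akathisia, elevated mood, insomnia.
- Total: 6 + 8 + 3 = 17.

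**Step 2. Set the triggers side by side.**

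| Protocol place | Trigger for stopping drug | Trigger for AESI report |
|---|---|---|
| Table 7-1 | any one of 17 findings | any one of 17 findings |
| 6.2.3.2 | clinical suspicion of the syndrome | the suspected event |
| 7.1.3 | none (refers to 6.2.3) | case judged possibly to be the syndrome |
| 7.1.3.2, after the table | none | event term recorded on clinical suspicion |
| 6.2.3, introduction | none | findings that fit the syndrome |

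**Step 3. Look for a rule of precedence.** None of these passages says that the table applies only after suspicion has arisen, or that one passage overrides another.

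**Step 4. Ask whether the row is confined to suspected cases.** Its middle column concerns every clinic visit, and Section 4.7.2 requires this monitoring for all subjects, whatever their serotonergic co-medication. The row therefore reaches routine visits.

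**Step 5. Compare the literal row with the rest of the protocol.**

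- Section 4.7.4 lists agitation, elation and nighttime behavior among the reasons for starting an antipsychotic during the extension, and allows benzodiazepines for agitation without ending participation.
- Section 4.7.5 allows medication at bedtime for sleep.
- Section 7.1.3.1 lists dizziness and tachypnea as signs of anemia.

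The protocol thus manages some of the 17 findings elsewhere without stopping drug, or links them to another condition.

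**Illustration only.** If each of the 17 findings were present at a visit with probability p, independently of the others, the chance of at least one would be 1 − (1 − p)^17:

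- p = 1%: 1 − 0.99^17 = 15.7%
- p = 2%: 1 − 0.98^17 = 29.1%
- p = 5%: 1 − 0.95^17 = 58.2%

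Both p and independence are assumptions; the documents support neither. Related findings, such as rigidity with hypertonia, would tend to occur together, and that lowers these values.

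**The case against.** The best reply is that the context settles the reading. The table is presented as a guide, and its title concerns the monitoring and management of the syndrome, which may presuppose that the syndrome is suspected. Section 6.2.3.2 cites Section 7.1.3.2 for guidance on assessment, and Section 7.1.3 sends dosing decisions back to Section 6.2.3. On this reading the signs prompt suspicion, and suspicion prompts action. That is a reasonable interpretation and many sites may adopt it. It does not remove the conflict: the row states no such condition, covers routine visits, and puts the action directly beside the list.

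The second reply is that the data would show any divergence. This stands in part. AESIs and withdrawals are tabulated by preferred term. SAP Listings 16.2.7.3.1 and 16.2.9.6 show the action taken, the AESI flag and each sign by subject and visit. The medical monitor is informed of AESIs (Section 7.1.3) and of dose decreases and interruptions (Section 6.2.2). A withdrawal for isolated insomnia should therefore be traceable. A reader might infer that the AESI results would be uninterpretable; these safeguards do not support that. What they cannot recover is how an investigator who followed the table would have judged the case under Section 6.2.3.2.

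A reader might also take SAP Table 14.3.4.4.1, which counts a subject with a yes "to any of the signs or symptoms on the Serotonin Toxicity (Syndrome) Assessment form", as the table's trigger carried into the analysis. It is not. It carries out the sign tabulation asked for in Protocol Section 9.6.5, and AESIs are reported separately.

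**Conclusion.** The protocol's conditions for these two actions conflict, and no passage resolves the conflict. The conclusion rests on the wording alone and needs no assumption about how often the signs occur. If sites read the passages differently, discontinuation would depend partly on site, and AESI counts and rates of withdrawal for adverse events might not be comparable across about 170 sites. Whether sites would in fact diverge, and by how much, cannot be known from the documents.

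A reader might infer from the illustration that 16% to 58% of subjects would be stopped or reported at a visit. The documents do not support that: the frequencies are assumed, independence is doubtful, and mere presence at a visit includes long-standing findings. The figures show only that a trigger of any one in 17 can be broad.

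**What to change.** Reconcile Table 7-1 with the introduction to Section 6.2.3, Section 6.2.3.2, Section 7.1.3 and the text of Section 7.1.3.2, so that one stated trigger governs discontinuation and one governs AESI reporting. State explicitly how the table's action column relates to Section 6.2.3.2. The sponsor's clinicians must decide what each trigger is; no clinical rule is proposed here.

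The SAP's AESI tables already take the protocol's definition and would follow the reconciled text. SAP Table 14.3.4.4.1 can stay as a separate tabulation of signs.

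The cost is a protocol clarification and a letter to sites. No new procedure, visit or data item is needed.
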